10.1.4.3 Imaging Assessments of Disease Status

All subjects will have a baseline skeletal survey. Repeat skeletal survey is recommended as clinically indicated.

Subjects with physical exam findings suggestive of plasmacytoma should undergo baseline imaging with computed tomography [CT] scan, magnetic resonance imaging [MRI], or positron emission tomography/CT [PET/CT].

Repeat plasmacytoma imaging is required only to confirm a response of PR or better, to confirm PD, or if clinically indicated. The same imaging technique should be employed for each measurement.

For study purposes, a plasmacytoma is considered measurable if the longest diameter is at least 1 cm and the product of the greatest orthogonal cross-diameters is at least 1 cm².

10.1.5 MYELOMA RESPONSE ASSESSMENT

Response will be determined by the investigator based on the disease assessments described above and the IMWG-URC (see definitions in [Appendix C](#)). Myeloma response laboratory studies will be drawn at the beginning of each cycle before treatment. The following confirmatory assessments are required for all response categories (stringent complete response [sCR], CR, VGPR, and PR) and progressive disease:

- All laboratory-based progressive disease and all responses require 2 consecutive assessments made at any time before initiation of any new (ie, off protocol) therapy. Confirmatory lab samples should be separated by at least 1 calendar day
- Progressive disease by nonlaboratory-based assessment (ie, plasmacytoma or skeletal lesion) does not require confirmatory report
- All response categories also require no evidence of progression including new bone lesions, if radiographic studies are performed
- Confirmation of CR or sCR requires local pathology review of a bone marrow biopsy or aspirate (a repeat confirmatory bone marrow sample is not required)
- Extramedullary plasmacytoma evaluation is required to confirm PR, CR, or sCR (if present at baseline; [Rajkumar, 2011](#))

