APPENDIX C INTERNATIONAL UNIFORM RESPONSE CRITERIA FOR
MULTIPLE MYELOMA

Summary of International Myeloma Working Group Uniform Response Criteria
(IMWG-URC)

Response Subcategory	Multiple Myeloma Response Criteria
sCR	
• Negative immunofixation on the serum and urine and• Disappearance of any soft tissue plasmacytomas and• < 5% plasma cells in bone marrow and• Normal SFLC ratio and• Absence of clonal plasma cells in bone marrow by immunohistochemistry or 2- to 4-color flow cytometry
CR	
• Negative immunofixation on the serum and urine and• Disappearance of any soft tissue plasmacytomas and• < 5% plasma cells in bone marrow• In patients with measurable disease only by SFLC, normal SFLC ratio
VGPR	
• Serum and urine M-protein detectable by immunofixation but not on electrophoresis or• $\geq 90\%$ reduction in serum M-component with urine M-component < 100 mg per 24 hours• In patients with measurable disease only by SFLC, a decrease $\geq 90\%$ in the difference between involved and uninvolved FLC levels, in addition to VGPR criteria, is required
PR	
• $\geq 50\%$ reduction of serum M-protein and reduction in 24-hour urinary M-protein by $\geq 90\%$ or to < 200 mg per 24 hours (if both are measurable at baseline)• In patients with measurable disease only by SFLC, a decrease $\geq 50\%$ in the difference between involved and uninvolved FLC levels is required in place of the M-protein criteria.• In addition to the above criteria, if present at baseline, $\geq 50\%$ reduction in the size of soft tissue plasmacytomas is also required.
Stable Disease	
• Not meeting criteria for CR, VGPR, PR, or PD

Summary of International Myeloma Working Group Uniform Response Criteria
(IMWG-URC) (cont'd)

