4.2 Subgroups

No subgroup analyses are planned in this study.

5. Definitions

Baseline

The baseline value is the closest recorded measurement prior to the first dose of study drug. If there are multiple valid records on an individual at the same date, then the record closest to cycle 1 day 1 will be used.

Best overall response by computational assessment

Best overall response will be derived using the Onyx Response Computational Assessment (ORCA) for multiple myeloma disease assessments based on the International Myeloma Working Group Uniform Response Criteria (IMWG-URC) ([Durie et al. 2006](#), with revisions, [Rajkumar, et al. 2011](#)). The detailed algorithm is documented in a separate document.

Best overall response by investigator assessment

Best overall response by investigator assessment is the best confirmed response by the analysis trigger date based on the responses by visit collected on myeloma response assessment CRF. The following confirmatory assessments are required for all response categories (sCR, CR, VGPR and PR) and PD:

- All laboratory-based progressive disease and all responses require two consecutive assessments made at any time before initiation of any new therapy. Confirmatory lab samples should be separated by at least one calendar day.
- Progressive disease by non-laboratory-based assessment (ie, plasmacytoma or skeletal lesion) does not require confirmatory report.
- All response categories also require no evidence of progression including new bone lesion, if radiographic studies are performed.
- Confirmation of CR or sCR requires local pathology review of a bone marrow biopsy or aspirate (a repeat confirmatory bone marrow sample is not required)
- Extramedullary plasmacytoma evaluation is required to confirm PR, CR, or sCR (if present at baseline)

Best overall response will be decided in the following order of confirmed responses: sCR, CR, VGPR, PR, SD, PD starting from the best to the worst.

End of Study Date for a Subject

The end of study date is the date recorded on the End of Study page for an enrolled subject.

First Dose Date

The first dose date is the date on which a subject is administered the first dose of any study drug.

Fluorescent in Situ Hybridization (FISH) Risk Group

Subjects in this study had FISH analysis performed by a central study laboratory and local laboratory.

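### VGPR carries no plasmacytoma size condition although PR does, so a subject who fails PR on a baseline plasmacytoma can still be a VGPR and count in ORR

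*Protocol*

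**What the plan says.** Four places bear on this.

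- **Protocol Appendix C (response criteria).** For PR, if a plasmacytoma was present at baseline, a 50% or greater "reduction in the size of soft tissue plasmacytomas is also required". For CR and sCR the condition is "Disappearance of any soft tissue plasmacytomas". The VGPR row has only M-protein and free light chain routes, the first being "Serum and urine M-protein detectable by immunofixation but not on electrophoresis" and the second a serum fall of at least 90% with urine below 100 mg per 24 hours. Stable disease is "Not meeting criteria for CR, VGPR, PR, or PD", so VGPR and PR are listed as separate alternatives.
- **Protocol 10.1.5.** The confirmation rules are introduced as covering sCR, CR, VGPR and PR, but the plasmacytoma bullet reads "Extramedullary plasmacytoma evaluation is required to confirm PR, CR, or sCR".
- **SAP Section 5 (best overall response by investigator).** The same list appears: "Extramedullary plasmacytoma evaluation is required to confirm PR, CR, or sCR (if present at baseline". Best response is then the highest confirmed category, with VGPR ranked above PR.
- **Protocol 10.1.4.3.** "Repeat plasmacytoma imaging is required only to confirm a response of PR or better, to confirm PD, or if clinically indicated". PR or better includes VGPR. No size threshold is given here.

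ORR (Protocol 13.1.2; SAP 2.1 and 9.5.1) counts sCR, CR, VGPR and PR. DOR (SAP 9.5.3) is computed for everyone with PR or better.

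**The concern.** A response scale should be nested, so that anyone who reaches a higher category also meets the lower one. Here the higher category omits a condition that the lower one imposes. For a subject with a baseline plasmacytoma, VGPR can be reached on M-protein alone while PR cannot.

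The three texts on confirmation also do not line up. The imaging section covers VGPR, and the two confirmation lists leave it out. A site that does image at VGPR finds no written rule for what to do with a lesion that is unchanged.

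At stake are ORR and the VGPR rate, which can only go up, and the composition of the DOR set. Efficacy rests on investigator assessment with no independent review committee (Protocol 13.3), so the wording that investigators follow matters.

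**Working it through.** The plan gives no figure on this point, so the check is a comparison of the criteria followed by the weight of one subject.

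**Step 1. Apply the written criteria to two subjects with the same unchanged baseline plasmacytoma.** Subject A: serum M-protein down 92%, urine below 100 mg per 24 hours. Subject B: serum M-protein down 60%, PR urine condition met.

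| Category (Appendix C) | Plasmacytoma condition | Subject A | Subject B |
|---|---|---|---|
| CR, sCR | must disappear | not met | not met |
| VGPR | none written | met | not met (serum fall under 90%) |
| PR | at least 50% reduction | not met (lesion) | not met (lesion) |
| PD | new lesion or at least 50% growth | not met | not met |
| Best response | | VGPR, ORR responder | SD, non-responder |

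Subject A fails PR, and fails it only on the lesion, but is ranked above PR.

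**Step 2. See whether another rule catches it.** Protocol 10.1.5 and SAP Section 5 require no evidence of progression for every response category. Appendix C defines plasmacytoma progression as a new lesion or growth of at least 50% in the sum of cross-products of measurable lesions. A stable lesion passes. For a measurable lesion, the gap therefore runs from less than 50% shrinkage to less than 50% growth. The SAP ranking of confirmed responses contains no rule that a VGPR must also satisfy PR.

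**Step 3. Endpoints touched.** ORR and the VGPR rate can only rise. CRR is not affected, because CR and sCR require disappearance. PFS is not affected, because it depends on progression and death. DOR gains subjects, and the documents do not determine the direction of that effect.

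**Step 4. Weight of one subject.** Change in ORR = 1/n, with n from SAP 9.1.

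- Arm 3: 1/33 = 3.0 points
- RRMM 70 mg/m² pooled (Cohort 2 + Arm 2): 1/46 = 2.2 points
- NDMM 70 mg/m² pooled (Arm 1 + Cohort 4): 1/18 = 5.6 points
- Arm 1 or Cohort 4 alone: 1/9 = 11.1 points

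**Step 5. How many subjects.** The documents do not give the share of subjects with a baseline plasmacytoma. If it were 5% to 10% (an assumption), Arm 3 would have 0.05 × 33 = 1.7 to 0.10 × 33 = 3.3 such subjects, roughly 2 to 3. That is the number exposed to the rule, so it is a ceiling under the assumption. To be reclassified, a subject must also have a confirmed VGPR-level biochemical response, less than 50% shrinkage, no progression, and no PR or CR at any time. Nothing in the documents gives a frequency for that combination.

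**The case against.** The strongest reply is that Appendix C presents itself as a summary of the IMWG criteria, and ORR is defined by those criteria. The appendix marks only its plasmacytoma rules for PD as the sponsor's own interpretation. If the cited criteria also leave VGPR without a plasmacytoma item, adding one would move the endpoint away from its stated definition. The sources are not available here, so this cannot be settled. This objection stands in part. It is why the fix lets the sponsor keep the row and report both versions. It does not remove the mismatch between 10.1.4.3 and the two confirmation lists.

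Second, a reader might infer that VGPR can be confirmed with no repeat imaging. The documents do not support that: "Repeat plasmacytoma imaging is required only to confirm a response of PR or better" includes VGPR, and the Appendix A schedule asks for a repeat evaluation to confirm response without exempting it. What is missing is the size condition and the entry in the confirmation lists. Nor do 10.1.5 and the SAP say that evaluation is not needed at VGPR. They leave it out, and a site that follows 10.1.4.3 satisfies all three texts.

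Third, the consequence is limited. ORR is a descriptive secondary endpoint in a Phase 1b safety study, and SAP 2.2 plans no formal hypothesis test. In Protocol Table 13 one responder separates the two final boundaries (25/38 = 65.8% against 26/38 = 68.4%), but those boundaries are nonbinding, so it would be wrong to say that a decision turns on this. This objection stands, and it limits the weight of the point.

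Fourth, the SAP repeats the ORR analysis with the ORCA algorithm. That algorithm is in a separate document, so it can be assumed neither to close the gap nor to share it.

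**Conclusion.** The gap holds on the text of both documents. PR has a plasmacytoma size condition, VGPR has none, and nothing makes VGPR depend on PR, so the scale is not nested for subjects with a baseline plasmacytoma. The imaging rule and the confirmation lists need reconciling whichever response rule is kept.

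The direction is certain: ORR and the VGPR rate can only be higher than under a nested scale. The size is not known. One subject is worth 2.2 points in the pooled RRMM 70 mg/m² group and 3.0 points in Arm 3. The 11.1 points in a group of nine reflects the small group and says nothing about how often the situation arises. A reader might infer that the reported ORR is materially inflated. The documents do not support that, since they give neither the number of subjects with baseline plasmacytoma nor the frequency of the discordant response, and the number affected is probably small.

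The conclusion rests on a literal reading of Appendix C and on the main analysis being by investigator assessment. It is worth correcting because the correction is cheap.

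**What to change.** 1. In Protocol 10.1.5 and SAP Section 5, list PR, VGPR, CR and sCR as the categories that need plasmacytoma evaluation, in line with 10.1.4.3.
2. In Appendix C and SAP Section 5, state that VGPR also requires the PR plasmacytoma condition when a plasmacytoma was present at baseline. If the sponsor prefers to keep the VGPR row as its summary of the IMWG criteria, report ORR and DOR both with and without the condition.
3. List separately the subjects with a baseline plasmacytoma who have no repeat imaging or a non-measurable lesion (Appendix C sets 1 cm as the limit). Do not automatically cap them at SD: a missing scan is not evidence of non-response, and a cap could downgrade true responders.
4. Check that ORCA treats VGPR in the same way, without presuming that it is wrong.

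Cost: one line in Appendix C and SAP Section 5, one added word in each confirmation list, a programming check and one listing. No new procedure is needed, because 10.1.4.3 already requires the imaging. The downside is that ORR may fall slightly.

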10.1.6 CLINICAL LABORATORY TESTS

Clinical laboratory assessments will include the following:

- Hematology: hemoglobin, hematocrit, white blood cell (WBC) with complete differential (total neutrophils, lymphocytes, monocytes, eosinophils, basophils), RBCs, platelet count
- Full serum chemistry panel: sodium, potassium, chloride, bicarbonate, blood urea nitrogen (BUN), creatinine, glucose, calcium, magnesium, phosphate, AST, ALT, total protein, albumin, alkaline phosphatase, total bilirubin, uric acid, and lactate dehydrogenase (LDH)
- Abbreviated chemistry panel: sodium, potassium, chloride, bicarbonate, BUN, creatinine, glucose
- Coagulation tests: prothrombin time, activated partial thromboplastin time, and international normalized ratio

Hematology and serum chemistry (full or abbreviated) will be performed at Screening, on Days 1, 8, and 15 of each cycle, and at EOT. On Days 8 and 15 of each cycle, from Cycle 2 onwards, an abbreviated serum chemistry panel may be performed. Coagulation will be performed at baseline and at EOT. For screening laboratory samples, historical panel may be used if within 21 days prior to dosing on Cycle 1 Day 1. Thereafter, hematology samples

may be obtained anytime within the 24 hours prior to the carfilzomib administration, and full or abbreviated chemistry panels may be performed up to 72 hours prior to carfilzomib administration.

10.1.7 ELECTROCARDIOGRAM

Twelve-lead electrocardiograms (ECGs) including corrected QT interval (QTc; representing the corrected duration of ventricular electrical activity) will be performed locally. These will be required in all subjects at Screening only. Additional ECG assessment is only required if clinically indicated

10.1.8 ECHOCARDIOGRAM

A 2-D transthoracic ECHO to assess LVEF will be performed in all subjects at Screening and at EOT. During the Dose-evaluation Component, an ECHO is also required at Cycle 2 Day 15, \pm 7 days. Additional ECHO assessment is only required for subjects who develop clinically significant congestive heart failure.

If transthoracic ECHO is not available, multigated acquisition (MUGA) will be acceptable for LVEF evaluation.

10.1.9 SUBJECT CONVENIENCE AND SATISFACTION

Subject convenience and satisfaction will be assessed in all subjects by questionnaire at Cycle 3 Day 1 and Cycle 18 Day 1 (see [Appendix D](#)). The questionnaire should be administered prior to treatment with carfilzomib.

10.2 CORRELATIVE STUDIES

It is recommended that samples for correlative studies be collected only after screening laboratories confirm study eligibility for the subject.

10.2.1 PHARMACOKINETIC MEASUREMENTS

For both the Dose-evaluation and the Dose-expansion Components, blood samples will be collected from all subjects **on Day 8 of Cycle 1** for determination of plasma concentrations of carfilzomib.

Blood samples will be collected at the following time points:

- Predose (within 5 minutes before start of carfilzomib infusion)
- 15 minutes (\pm 5 minutes) after the start of carfilzomib infusion
- Immediately prior to (within 2 minutes before) the end of carfilzomib infusion
- 15 minutes (\pm 5 minutes) after the end of carfilzomib infusion
- 60 minutes (\pm 5 minutes) after the end of carfilzomib infusion

The actual time of PK sample collection will be recorded. Samples should be collected within a \pm 5 minute time window around the nominal time points (except for the time point immediately prior to the end of carfilzomib infusion in which the PK collection needs to occur prior to end of infusion). Collecting PK samples at times other than nominal time points will not constitute a protocol deviation. These samples will be assessed at a central laboratory. Directions for collection, processing, and shipping of PK blood samples are provided in the central laboratory manual.

10.2.2 PHARMACODYNAMIC MEASUREMENTS

For pharmacodynamic measurements, whole blood will be collected from the subjects on the following schedule:

For the Dose-evaluation component Cohorts 1 and 2, **and the first 8 subjects enrolled into Dose-expansion Arm 3**, whole blood will be collected. **On Days 1 and 8 of Cycle 1, whole blood will be collected pre-carfilzomib dose and post-carfilzomib dose.** On Days 9 and 11 of Cycle 1, when carfilzomib is not administered, one PDn sample will be collected at approximately the same time as when the pre-infusion sample was taken on Day 8.

Directions for collection, processing, and shipping of PDn samples are provided in the central laboratory manual.

10.2.3 FLUORESCENT IN SITU HYBRIDIZATION (FISH) TESTING

Bone marrow aspirate from all subjects will be evaluated centrally, at baseline, by FISH. Directions for collection, processing, and shipping of FISH samples are provided in the central laboratory manual.

10.2.4 MINIMAL RESIDUAL DISEASE

Analysis of MRD status will be performed by the central laboratory on all subjects by 2 methods:

Flow cytometry (FC) of cell surface markers and

NGS of DNA and/or RNA from the Ig locus.

The MRD analysis by FC will be performed on bone marrow aspirate samples collected at 2 time points: Cycle 8 Day 1 and upon achieving a CR or sCR. The MRD analysis by NGS will be performed on blood and bone marrow aspirate samples collected at 3 time points: baseline, Cycle 8 Day 1, and upon achieving a CR or sCR.

Directions for collection, processing, and shipping of MRD samples are provided in the central laboratory manual.

10.2.5 OPTIONAL GENOMIC BIOMARKERS

Analysis of genetics, gene expression, and cell surface biomarkers that may be predictive of response and resistance to treatment with proteasome inhibitors will be performed.

Exploratory studies will be conducted on all subjects who consent to optional genomic biomarker analysis. These analyses will be performed on bone marrow aspirate at baseline (the remaining portion of the bone marrow aspirate sample left after the amount required for FISH analysis has been collected at baseline), as well as a sample of blood and saliva also collected at baseline. At disease progression, an additional bone marrow sample for biomarker analysis may be collected from all subjects who consent.

Whole genome sequencing (WGS), whole exome sequencing (WES), whole transcriptome sequencing (RNA-Seq), and/or other methods of nucleic acid and protein quantification will be conducted on isolated tumor (CD138+) cells from bone marrow samples taken at baseline and disease progression. In addition, WGS or WES will be performed on a normal tissue sample (eg, CD3+ T cells isolated from peripheral blood or saliva) to distinguish germ line mutations from somatic mutations in tumor cell samples.

Directions for collection, processing, and shipping of optional genomic biomarker samples are provided in the central laboratory manual.

11 STUDY DISCONTINUATION

11.1 WITHDRAWAL OF SUBJECTS FROM TREATMENT

Subjects may withdraw from study treatment at any time. Reasons for discontinuation include:

- Adverse event
- Allogeneic stem cell transplant
- Pregnancy
- Death
- Lost to follow-up
- Noncompliance
- Withdrawal by subject
- Study terminated by the sponsor
- Physician decision
- Progression of disease
- Other

The primary reason for treatment discontinuation will be documented in the eCRF.

Investigators will be instructed to interview subjects to obtain the most accurate reason for study treatment discontinuation while respecting the privacy of the subject.

If the reason for treatment discontinuation is the occurrence of an AE, the subject will be followed by the investigator until such event(s) resolve, stabilize, and, according to the investigator's judgment, there is no need of further follow-up.

Treatment discontinuation due to progression should be recorded as "Disease Progression." If the Disease Progression meets any of the serious criteria, as outlined in [Section 12.2.1.4](#), then it should also be recorded as a serious adverse event (SAE) in the AE eCRF.

Sponsor or designee must be notified within 24 hours if a subject is withdrawn from treatment.

All subjects who withdraw or are withdrawn from study treatment will be encouraged to complete all relevant safety assessments and continue in the Active Follow-up period.

11.2 WITHDRAWAL OF SUBJECTS FROM STUDY

Reasons for complete withdrawal from the study (treatment and all follow-up) before documentation of subject death include:

- Withdrawal of consent by subject for all study procedures
- Lost to follow-up
- Sponsor decision

The reason for complete withdrawal from study will be documented in the eCRF.

11.3 STUDY TERMINATION

The sponsor has the right to terminate this study or a study site from participating in a study at any time. Reasons for study termination may include:

- The incidence or severity of AEs in this or other carfilzomib studies indicates a potential health hazard to subjects
- Subject enrollment is unsatisfactory
- Data recording is inaccurate or incomplete
- Investigator does not adhere to the protocol or applicable regulatory requirements in conducting the study

